## Biomedical Development Corporation

### BACKGROUND

Drug overdose is the leading cause of accidental death in the US, with opioids being the most common drug. Opioid addiction is driving this epidemic, with 20,101 overdose deaths related to prescription pain relievers, and 12,990 overdose deaths related to heroin in 2015. In 2014, an estimated 1.9 million people had an opioid use disorder related to prescription pain relievers and an estimated 586,000 had an opioid use disorder related to heroin use. The economic impact of illicit prescription opioid abuse alone is estimated to be \$53-72 billion, placing significant demands on our health care system and burdening society as a whole.

In previous work, we developed KIOS, an innovative software platform derived from nonlinear control theory. KIOS tracks multiple interacting symptoms to map patient trajectories and deliver evidence-based intervention strategies responsive to the specific needs of individuals. Accessible via computer or mobile devices, KIOS provides patients real time advice and reinforcement of lifestyle interventions to improve self-management. KIOS also can provide between-visit reporting to clinicians via downloadable reports or direct online monitoring.

By processing patient-entered assessment data in real-time via mobile devices, KIOS can provide early interventions for patients who exhibit elevated risk. KIOS provides responsive advice to patients to reinforce healthy practices, fostering self-management and adherence to treatment plans. KIOS is able to identify subtle changes in individual behavior when they first occur making it is possible to provide early warnings and intervention advice to guide the patient's trajectory. These early interventions reduce risk factors, prevent worsening of severity, and ultimately decrease resource utilization.

### STUDY PROTOCOL

This study consists of a beta test of the KIOS software. Participants in the beta test (n=20) will be invited to participate by Community Medical Services, an opioid treatment clinic located in San Antonio, TX.

**Beta Test.** Twenty individuals in recovery from opioid use disorder will be recruited from the community to participate in a beta test. Study participants must meet the following inclusion criteria: (1) male or female outpatients 18 years of age or older; (2) currently enrolled in an opioid treatment program and receiving medication assisted treatment for OUD; (3) currently stable in OUD outpatient treatment for 4 weeks or longer; and (4) ability to access KIOS-OUD via computer, smartphone, or tablet. Participants will be excluded if they (1) are unwilling or unable to comply with study requirements; (2) have an unmanaged major psychiatric illness (e.g., schizophrenia, major depressive disorder, bipolar disorder) or suicidality.

Participants will be enrolled in a 4-week single group pre-post evaluation of the intervention. The primary outcome will be user satisfaction as measured by use, usability and utility. Secondary outcomes include self-reported opioid use, depressive symptoms (as measured by the PHQ-9), and Quality of Life (as measured by WHOQOL-BREF).

Due to COVID-19, the beta test will be conducted primarily online and via telephone, including the consent process. All participants will attend an online orientation on Zoom to learn how to access and use KIOS, and participate in a training session. Prior to the online orientation but after consent has been obtained, participants will be asked to complete baseline PHQ-9 and WHOQOL surveys which will be converted to an electronic version and completed online. After the four-week evaluation phase, participants will complete a second round of surveys and participate in a final online debriefing session via Zoom. This approach permits social distancing while enabling users to be adequately trained while also evaluating KIOS-OUD within their typical environment rather than in a lab setting.

**Use.** Study participants will be asked to complete KIOS assessments online at least three times per week, but no more than once daily. KIOS may still be accessed by participants as many times as desired to review advice and graphs. All logins and assessments will be recorded on the KIOS server to tabulate frequency of use.

**Usability.** Evaluated at the end of the 4-week trial, the Systems Usability Scale-Modified (SUS), a single-factor, 10-item self-report scale will be used to evaluate participants' subjective experience using KIOS. The SUS will be converted to an electronic version and completed online. Participants will rate a set of statements related to their experience in the study. For example, "I needed to learn a lot of things before I could get going with this program." Items will be evaluated using a 5 point Likert-type scale (1 = strongly disagree; 5 = strongly agree). Higher scores out of 0 - 100 indicate greater usability. Generally, systems in early development may expect to have a rating of 30, while more mature systems should rate between 60 - 80. The SUS has demonstrated good reliability ( $\alpha = 0.91$ ) and validity.

**Utility.** After the 4-week trial, study participants will complete an additional questionnaire focusing on health metrics specific to KIOS. This survey will include questions regarding: (1) the content, appropriateness and relevance of the advice; (2) enhancement of self-management skills; (3) self-awareness and (4) overall satisfaction with health. Open ended questions will be asked to solicit suggestions, criticisms and comments. This survey will be completed online as well.

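### Self-reported opioid use is a secondary outcome of a single-group pre-post evaluation, but the protocol schedules no pre-KIOS value and names no instrument, recall period or time point for it

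*Protocol*

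**What the plan says.** The Beta Test part of the protocol's STUDY PROTOCOL section sets the design: "Participants will be enrolled in a 4-week single group pre-post evaluation of the intervention". It then lists the secondary outcomes, with opioid use first: "Secondary outcomes include self-reported opioid use, depressive symptoms (as measured by the PHQ-9", followed by quality of life on the WHOQOL-BREF. Two of the three are tied to a named questionnaire. Opioid use is described only as self-reported.

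The order of data collection is given in the same section. Before training: "Prior to the online orientation but after consent has been obtained, participants will be asked to complete baseline PHQ-9 and WHOQOL surveys". At training: "All participants will attend an online orientation on Zoom to learn how to access and use KIOS". At the end: "After the four-week evaluation phase, participants will complete a second round of surveys", with no list of what that round contains.

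The paragraph headed Use asks for KIOS assessments several times a week and says they are logged so that frequency of use can be counted. The Usability and Utility paragraphs add two questionnaires, both given only at the end.

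**The concern.** In a single-group study each participant's own value before the intervention is the only comparator. If it is not collected before KIOS starts, a later analysis plan cannot restore it: such a plan decides how data are analysed, not what participants were asked at the outset.

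The protocol does specify what is asked at baseline, and opioid use is not in that list. It is also the only listed outcome that directly measures the behaviour a tool for opioid use disorder is meant to influence. Followed as written, the study could end with pre and post values for mood and quality of life, and with no assured way to say whether opioid use differed from before KIOS.

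**Working it through.** No arithmetic applies beyond a count, and the protocol gives no figure to reproduce. The check matches each secondary outcome to every data collection that the protocol describes.

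| Secondary outcome | Named instrument | Before orientation | During the 4 weeks | After the 4 weeks |
|---|---|---|---|---|
| Depressive symptoms | PHQ-9 | Scheduled | Not stated | Implied by the second round |
| Quality of life | WHOQOL-BREF | Scheduled | Not stated | Implied by the second round |
| Self-reported opioid use | None | Not scheduled | Not stated | Not stated |

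So 2 of 3 secondary outcomes have a scheduled pre-KIOS value, and 3 - 2 = 1 does not.

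Each other possible source of a pre-KIOS value was then considered.

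1. **PHQ-9 and WHOQOL-BREF.** The protocol assigns these to depressive symptoms and quality of life, not to opioid use.
2. **Usability scale and utility questionnaire.** Both are given only at the end. The first concerns the experience of using the program. The topics listed for the second are the advice, self-management, self-awareness and satisfaction with health. Neither is described as covering opioid use.
3. **KIOS assessments.** BACKGROUND says that "KIOS tracks multiple interacting symptoms to map patient trajectories" and that it works "By processing patient-entered assessment data in real-time via mobile devices". An opioid-use item would fit that description, but none is named, no look-back period is given, and the stated reason for logging assessments is to count use of the software. Participants learn to access KIOS at orientation, so the earliest entry comes at or after it. Such an entry is a pre-KIOS value only if the item looks back over the time before access.
4. **Eligibility.** Participants must have been stable in outpatient treatment for at least four weeks. This is an entry condition; it records no level of opioid use and is not defined as abstinence.

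None of the four supplies a scheduled pre-KIOS value.

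A further point concerns wording. Every participant is "receiving medication assisted treatment for OUD". A bare question about opioid use could be read to include that medication, so whatever item is used has to separate the two.

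**The case against.** The strongest case against has four parts.

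*The protocol never promises an analysis of change in opioid use.* This is true. It lists the outcome and states no estimate or test. The pre-post label does not bind every outcome either, since the usability and utility measures are post-only. Those two, however, ask about experience with KIOS and its advice, for which a prior value makes little sense. Opioid use exists before KIOS and is grouped with two outcomes that do get a baseline. The point therefore stands in conditional form: if change is intended, its pre value is not scheduled.

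*KIOS itself may be the source.* This is plausible. The outcome is self-reported with no named questionnaire, and the version under test is the one for opioid use disorder. Orientation includes a training session, and the protocol does not say whether a first assessment is entered there. A reader might infer that every KIOS entry falls after orientation, or that no usable pre-KIOS value could exist; the protocol establishes neither. What stands is that such a value is not assured.

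*The gap is not only at baseline.* This is also right. The contents of the second survey round are not listed, so a post value for opioid use is not explicitly scheduled either. The point covers both ends.

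*The consequence is small.* This is a 20-person software beta test with user satisfaction as its primary outcome. That limits the severity but does not remove the gap.

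**Conclusion.** The concern holds in a limited form. The protocol lists self-reported opioid use as an outcome of a single-group pre-post evaluation, schedules a pre-orientation value for the other two secondary outcomes only, and gives no instrument, recall period or time point for opioid use. Without a pre-KIOS value, change cannot be assessed, because there is no control group to stand in for it. In-study use could still be described if it is recorded.

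The impact is minor to moderate. The primary outcome and the PHQ-9 and WHOQOL-BREF outcomes are unaffected.

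The conclusion rests on two readings: that change in opioid use is of interest, as the design label and the neighbouring outcomes suggest, and that KIOS use does not begin before orientation.

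A reader might infer that the protocol contradicts itself, or want a numerical size for the error. The text does not support either. Listing an outcome without a schedule is a gap rather than a contradiction. The protocol gives no expected level of opioid use and no test for it, so any range of possible change would come from assumed figures.

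**What to change.** Add one self-reported opioid-use item to the online surveys completed after consent and before orientation, and the identical item to the second round after four weeks. State its recall period, and word it so that non-prescribed use is kept apart from the treatment medication. The recall period at the second round should not reach back before orientation, or the two values will overlap. Report the paired change descriptively. If KIOS entries also record opioid use, say so and treat them as supplementary.

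If only use during the study is of interest, one sentence is enough: this outcome is descriptive, and no pre-post conclusion will be drawn from it. The protocol should then also say where and when it is recorded.

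The cost is one extra question in two surveys already planned and a sentence of protocol text, with no additional session or participant. The downside is that in 20 participants already stable in treatment the estimate of change will be imprecise, which is a reason to keep it descriptive.

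### A participant who withdraws before week 4 contributes no usability rating, no utility rating and no comment, because all three are collected only once the four weeks are over

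*Protocol*

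**What the plan says.** All references are to the STUDY PROTOCOL section of the Protocol.

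- **Beta Test** defines the primary outcome: "The primary outcome will be user satisfaction as measured by use, usability and utility". Twenty people are enrolled for four weeks in a single group. Baseline surveys are the PHQ-9 and the WHOQOL only. After the four weeks, participants complete a second round of surveys and "participate in a final online debriefing session via Zoom".
- **Use** is recorded continuously: "All logins and assessments will be recorded on the KIOS server to tabulate frequency of use".
- **Usability** is the SUS, "Evaluated at the end of the 4-week trial". On its format: "The SUS will be converted to an electronic version and completed online".
- **Utility** has its own survey: "After the 4-week trial, study participants will complete an additional questionnaire". The same paragraph adds: "Open ended questions will be asked to solicit suggestions, criticisms and comments". This survey is also online.

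None of these paragraphs mentions an interim rating, an exit survey or any feedback at withdrawal.

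**The concern.** Two of the three primary components, and both channels for free comment, depend on the participant still being in the study after week 4. People who dislike a piece of software may be more likely to leave a study of it. If so, the SUS score, the utility ratings and the written criticisms come from a favourable subset.

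The protocol has to settle this, because it is a matter of collection. An analysis plan can say how missing ratings are handled, but it cannot create ratings or comments that nobody asked for. A beta test that sets out to gather criticism would lose it from the people with the most reason to give it. With 20 participants, each one carries 1/20 = 5% of the mean.

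**Working it through.** The protocol states no withdrawal rate, expected SUS score or success threshold, so there is no figure of its own to reproduce. The check has two parts.

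**1. What is collected from someone who withdraws before week 4**

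| Source | When collected | Available from an early withdrawal? |
|---|---|---|
| Use (server logs) | continuously | yes, up to leaving |
| SUS | end of week 4 | no |
| Utility survey | after week 4 | no |
| Open-ended questions | within the utility survey | no |
| Debriefing | after week 4 | no |
| Baseline PHQ-9, WHOQOL | before orientation | yes, but they do not rate KIOS |

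The logs show that someone stopped logging in. They do not show whether that person withdrew, how they rated KIOS, or why they left.

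**2. How much the SUS mean could be affected (illustration)**

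Inputs from the protocol: 20 enrolled; SUS scored 0 to 100; reference ratings of 30 for early systems and 60 to 80 for mature ones.

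Assumed inputs: k participants missing; responder mean m of 65 to 75, inside the 60 to 80 band; mean s of the missing ratings 30 to 50, with 30 being the protocol's figure for early systems.

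All-enrolled mean = [(20 − k)·m + k·s]/20 = m − (k/20)(m − s)

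Overstatement by the responder mean = (k/20)(m − s)

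The smallest gap m − s is 65 − 50 = 15 and the largest is 75 − 30 = 45.

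| k missing | k/20 | Smallest | Largest |
|---|---|---|---|
| 0 | 0 | 0 | 0 |
| 1 | 0.05 | 0.05 × 15 = 0.75 | 0.05 × 45 = 2.25 |
| 2 | 0.10 | 0.10 × 15 = 1.5 | 0.10 × 45 = 4.5 |
| 4 | 0.20 | 0.20 × 15 = 3.0 | 0.20 × 45 = 9.0 |

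One case in full: with m = 70, s = 30 and k = 4, the mean over all 20 is (16 × 70 + 4 × 30)/20 = (1120 + 120)/20 = 62. The responder mean of 70 overstates it by 8.

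The direction comes from assuming s below m. Without that assumption, the missing ratings could lie anywhere from 0 to 100. With m = 70 and k = 2, the all-enrolled mean lies between 1260/20 = 63 and (1260 + 200)/20 = 73. With k = 4 it lies between 1120/20 = 56 and (1120 + 400)/20 = 76. Both ranges include 70, so the document alone fixes neither size nor sign.

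No such calculation is possible for utility, because the text gives no score for it.

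**The case against.** The strongest case against is that the protocol is silent on withdrawal rather than wrong about it. One rating at the end of exposure is a natural choice: the SUS and the utility questions ask about experience that takes time to build, and a rating after a few days measures something different. The gap is also narrow. The study is short and mostly remote, entry requires stable treatment, and people unwilling or unable to meet the study requirements are excluded, so withdrawals may be few. Title and consent pages were not available, and withdrawal arrangements could be described there.

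Much of this stands. The absence is confirmed only for the text reviewed, the number of withdrawals may be zero, and early ratings should not simply be mixed into the week-4 result. It does not remove the point. The protocol does fix when these ratings are taken, and that time is one an early withdrawal never reaches.

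A reader might infer more than the document supports:

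- *That everyone who disengages is lost.* The wording has study participants complete the surveys, which covers people who stop using KIOS but remain enrolled. Only those who withdraw are affected.
- *That the whole primary outcome ignores dropout.* Use is logged up to the time a person leaves.
- *That the SUS result will be inflated, or that falling below 60 would change a conclusion.* Nothing in the text links withdrawal to dissatisfaction. The benchmark sentence, "systems in early development may expect to have a rating of 30, while more mature systems should rate between 60 - 80", describes typical scores and sets no success criterion. In an adverse case (m = 65, s = 30, k = 4) the mean would be 65 − 0.20 × 35 = 58, but no decision hangs on it.

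**Conclusion.** The point holds as a minor, inexpensive improvement to data collection. As the reviewed text stands, two of three primary components and all free-text and debriefing feedback are missing for anyone who withdraws before the end of week 4, and this cannot be repaired afterwards.

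The consequence is conditional. It needs at least one withdrawal, and it biases the ratings only if those who leave would have rated KIOS differently. Under the stated assumptions the SUS mean is overstated by 1.5 to 4.5 points with 2 of 20 missing and by 3 to 9 points with 4 of 20 missing. These figures show scale and are not estimates. The loss of comments does not depend on any assumed score: each withdrawal loses that person's reasons.

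**What to change.** In the Usability and Utility paragraphs, state that anyone who withdraws before week 4 is offered the same online SUS and utility forms, including the open-ended questions, at withdrawal. For reporting:

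- keep the week-4 summary as the main result;
- report the early ratings separately, with each person's time on KIOS;
- state how many withdrew and how many of those responded;
- show one sensitivity summary that pools early and week-4 ratings.

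The cost is about one sentence in each paragraph plus a short reporting statement. No new instrument is needed, since both forms are already planned for online completion. The drawbacks are a few ratings after shorter exposure, some refusals among those who leave, and a pooled summary that may be less favourable than the week-4 one.

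### Do the two general SUS reference levels (30, or 60 to 80) let almost any usability result pass as expected?

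*Protocol*

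**What the plan says.** The STUDY PROTOCOL section describes the design in one sentence: "Participants will be enrolled in a 4-week single group pre-post evaluation of the intervention". It sets the endpoint in another: "The primary outcome will be user satisfaction as measured by use, usability and utility". Twenty people are to be recruited.

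The Usability paragraph covers the second of the three components. The SUS is "a single-factor, 10-item self-report scale", answered from 1 to 5, scored from 0 to 100 with higher meaning more usable, and completed once after the four weeks. Among these descriptive details, in a sentence that opens by marking itself as a generality, it adds that "systems in early development may expect to have a rating of 30, while more mature systems should rate between 60 - 80". Reliability and validity follow.

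The paragraph does not place KIOS-OUD in either group and sets no SUS level as success. Two other statements bear on its stage of development. BACKGROUND says "In previous work, we developed KIOS, an innovative software platform derived from nonlinear control theory", while STUDY PROTOCOL calls the study a beta test.

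**The concern.** The design is labelled pre-post, but the SUS has no pre-value, because it is completed only after four weeks of use. With no comparator either, a SUS mean can be read only against something outside the study. The protocol offers two reference levels, 30 points apart, with nothing said about scores between 30 and 60. The cues on maturity point both ways: a platform built earlier, now in beta test. Someone could therefore choose the label after seeing the score.

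The lower level also looks too lenient to screen anything, because it sits on the unfavourable half of the scale. If 30 were read as a floor to be cleared, a product that users rate below neutral could be reported as doing as well as expected. A primary component would then say little about whether the software needs more work.

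**Working it through.** The protocol gives no SD, power or precision statement, so there is no figure of its own to reproduce. The checks below use its scale and sample size, with the SD assumed.

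**1. What 30, 60 and 80 mean on the scale.** Inputs from the Usability paragraph: ten items, responses 1 to 5, total 0 to 100. Assume linear scoring, with every item turned in the favourable direction. Then SUS = 100 × (item sum − 10) / 40, so mean item = 1 + 4 × SUS/100.

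| SUS | Mean item |
|---|---|
| 30 | 2.2 |
| 50 | 3.0 (all answers neutral) |
| 60 | 3.4 |
| 80 | 4.2 |

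So 30 is below neutral. To call it unusable would go further than the scale supports.

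**2. Precision with 20 participants.** Half-width = t(0.975, 19) × SD/√20.

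| Assumed SD | Half-width | 95% CI, observed mean 30 | 95% CI, observed mean 45 |
|---|---|---|---|
| 15 | 7.0 | 23.0 to 37.0 | 38.0 to 52.0 |
| 20 | 9.4 | 20.6 to 39.4 | 35.6 to 54.4 |
| 25 | 11.7 | 18.3 to 41.7 | 33.3 to 56.7 |

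**3. Would the choice of level matter if it were a rule?** Yes. Take a true mean of 45 and the normal approximation, with SE = SD/√20. At SD 20 the observed mean reaches 30 with probability 0.9996 and reaches 60 with probability 0.0004. At SD 25 the figures are 0.9964 and 0.0036.

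**4. Is it a rule?** The text does not make it one. The sentence is a general remark placed between the score direction and the reliability figure, and it does not mention KIOS. Nor does it call 30 a minimum, and the claim that almost any score would pass depends on that reading. Taken literally, a mean of 45 fits neither description, and its intervals in step 2 exclude both 30 and 60. A mean of 30 has an interval wholly below 50 at every SD shown, so the result itself would reveal an unfavourable rating.

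**5. Does the primary outcome rest on a SUS cut-off?** It does not. In the same section:
- Use is logged on the server. The request of at least three assessments a week gives 3 × 4 = 12 over the study as a natural reference, although it is an instruction to participants and not a success level.
- The Utility survey asks about the content and relevance of the advice and has open-ended questions that invite criticism.
- A debriefing session follows the evaluation phase.

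Each of these can show a need for rework. The protocol mentions no later trial and no go/no-go decision that would depend on a SUS threshold.

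**6. Would fixing 60 as the standard be a clear gain?** If the observed mean must reach 60, a product with a true mean of exactly 60 passes about half the time. If the lower confidence limit must reach 60, the observed mean has to be about 60 + 9.4 = 69.4 at SD 20. The sample separates 30 from 60 easily, but that says nothing about how well it decides near 60.

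**The case for a change.** The best case for acting is that a reference level in a protocol gets used, whatever its grammar. These are the only benchmarks attached to any primary component of an uncontrolled study. They are far enough apart for the choice to settle the reading (step 3), and the choice can be made after the data are in. One sentence would prevent that at almost no cost.

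Part of this stands. The protocol does not say which level is relevant to KIOS-OUD, and a reader who treats 30 as a floor would be using a lenient one. The harm does not follow, because the protocol neither adopts 30 as a standard nor makes the primary outcome depend on it. Nor is it plain that the upper band is the right one. BACKGROUND speaks of the KIOS platform in general, whereas the product under test is KIOS-OUD in a 20-person beta test. Reasonable statisticians would differ on holding such a product to the bound for mature systems. Making the SUS the lead component would restructure the primary outcome, which this ambiguity does not require.

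**Conclusion.** The concern is right on its facts but does not call for a change. Two general SUS levels are quoted without assigning KIOS-OUD to either, and the lower one maps to 2.2 on the item scale against a neutral 3. But they are background to the instrument and not a decision rule. Following the plan still yields a sound SUS mean. With 20 participants its 95% half-width is about 9 points at SD 20, and 7.0 to 11.7 across SD 15 to 25. That is enough to show whether users rate the software clearly below neutral.

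What remains is a success criterion that the protocol does not write down. A SAP, not at hand here, would commonly supply it, and an analyst can sensibly report the mean with its interval beside both levels. The conclusion rests on linear scoring of the ten items and on the assumed SDs. The reading of the sentence as background depends on neither.

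### Does a health-satisfaction topic in the utility survey contaminate the primary outcome of user satisfaction with KIOS?

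*Protocol*

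**What the plan says.** All of this is in the Protocol, under STUDY PROTOCOL. The Beta Test paragraph defines the main endpoint: "The primary outcome will be user satisfaction as measured by use, usability and utility". It describes the design as a "4-week single group pre-post evaluation of the intervention", with 20 participants who must be "currently enrolled in an opioid treatment program and receiving medication assisted treatment for OUD". It names the surveys given before the orientation session: "participants will be asked to complete baseline PHQ-9 and WHOQOL surveys". Opioid use, PHQ-9 and WHOQOL-BREF are secondary outcomes.

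The Use paragraph counts logins and assessments on the KIOS server. The Usability paragraph gives the SUS at the end of the four weeks, to capture the participant's "subjective experience using KIOS".

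The Utility paragraph opens: "After the 4-week trial, study participants will complete an additional questionnaire focusing on health metrics specific to KIOS". It then lists four topics. The first is "1) the content, appropriateness and relevance of the advice", the second is improvement in self-management skills, the third is self-awareness, and the fourth is "4) overall satisfaction with health". Open-ended questions for criticism and suggestions complete the survey. No item wording, response scale or scoring rule is given.

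**The concern.** The primary outcome is meant to be satisfaction with a piece of software. The other measures are visibly about that software: server records of KIOS use, a usability scale about using KIOS, and questions on the advice that KIOS gives. The fourth utility topic, as labelled, is about health and names neither KIOS nor a change.

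If the item simply asked how satisfied participants are with their health, the answer could part company with their opinion of KIOS. Someone doing well on medication assisted treatment could score high and find the software useless; someone in poor health could score low and find it helpful. There is no control group, and the questionnaire is not among the surveys named at baseline, so nothing in the design would separate the two. A health rating would then be reported under the primary outcome, while the protocol's other measures of participant status are secondary. Analysis could not repair this afterwards, because the question asked and the time of asking are settled once the data are in.

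**Working it through.** The protocol gives no figure to reproduce, so the check is a reading of the relevant statements against one another.

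1. **What is fixed.** The Utility paragraph names subjects on which questions will be asked. It does not give the questions. The concern needs the fourth item to be a plain rating of health, and the protocol neither says that nor rules it out.

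2. **What the lead-in does.** The sentence introducing the questionnaire says that it concentrates on measures of health particular to KIOS. That description covers all four topics. The natural reading of the fourth is therefore satisfaction with health in connection with using KIOS, although a reader could take the phrase to mean health ratings in general.

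3. **Whether the fourth label stands out.** Neither the second topic (self-management skills) nor the third (self-awareness) names the product. All three labels are shorthand. If the lead-in supplies the link to KIOS for the second and third, it supplies it for the fourth.

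4. **Whether a baseline is needed.** Participants cannot rate a product's usefulness before using it. The SUS is also given only at the end, which is appropriate for the same reason. The before-and-after part of the design rests on PHQ-9 and WHOQOL, which are collected at baseline and included in the later round of surveys. The protocol states no comparison, hypothesis or claim of change for the utility survey, so a missing baseline undermines no stated conclusion.

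5. **How much is exposed.** At most one topic of four, in one component of three, with n = 20. The server counts and the SUS do not depend on it. The protocol does not combine the four topics into a score, does not combine use, usability and utility into a single number, and sets no threshold for success. If the topics are reported one by one, the fourth cannot alter the results for the other three, so the distortion is zero. Any other figure would first require inventing a scoring rule, and would describe that invention and not this trial.

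**The case for a change.** The strongest case for acting is that the lead-in does not settle the matter, that a check would cost almost nothing, and that an analysis plan cannot rescue a badly worded item. If the item is already tied to KIOS, the label should say so; if it is not, the item needs rewording before anyone answers it. The protocol also places participant status among the secondary outcomes, so a general health rating would be in the wrong place.

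Part of this stands. The label is ambiguous, and item content cannot be mended after collection. It is also true that a literal health rating, taken once in a single treated group, says little about the software. But each of these harms depends on an item that the protocol does not show being written in the less sensible of two ways, against the description that introduces it. The argument from attribution and change further assumes a purpose that the protocol does not give this questionnaire. What is left is a request to spell out item wording, which is a detail and not a mistake in the plan.

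**Conclusion.** The concern does not call for a change to the plan. The label of the fourth utility topic is loose, but the protocol does not show that the questionnaire lacks a link to KIOS, and its own introduction to the survey supplies one. A single administration after use suits product feedback in a beta test.

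The possible effect is confined to one of four topics in one of three components among 20 participants. Its size and direction cannot be derived, because no score is stated; with topic-by-topic reporting it is nil. No stated result or conclusion would be wrong.

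This rests on two assumptions. The first is that the survey's authors write the items, as the lead-in indicates, about what KIOS contributed. The second is that the topics are not merged into an unstated composite. If the fourth item did turn out to be a general health rating, an analyst would sensibly show it beside WHOQOL-BREF and not count it as satisfaction with the software.
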